Cover Page for Clinical Trial Study

Official Title: Comparing the Effects of a Plush Toy Dog versus a Live Therapy Canine on
Prosocial Behavior and Emotional Regulation in Children with Autism Spectrum Disorder

NCT#: N/A

Date: March 13, 2025

Study Protocol

Clinical Study Description

The purpose of this project is to investigate the human-animal interaction (HAI) and bond (HAB) between a canine trained in therapy techniques or a canine plush toy and youth with autism spectrum disorder (ASD) during animal-assisted therapy (AAT) sessions. We seek to explore identified gaps in knowledge pertaining to AAT in pediatric ASD care management.

Specifically, we want to document human interaction between either a live canine or the plush toy canine during AAT sessions, evaluating behaviors observed during and after AAT sessions. Caregivers were given the option to enroll the child in the AAT study at the follow-up appointment after the diagnostic assessment was completed, or upon enrollment in the ASD program if the child had an ASD diagnosis. The study was conducted between June 2022 through August 2024. Each AAT study lasted between eight to 12 weeks, and caregivers had the option to re-enroll the child for the next study to continue addressing behavioral concerns.

Participants were divided into two groups: one with a therapy canine and one with a plush toy dog. Therapy sessions lasted 30 to 45 minutes, depending on the age and ability of the participant. All participants, no matter their group, received the same therapeutic strategies, such as sensory integration therapy and seated activity with the therapist, who is a certified pediatric nurse practitioner. Sessions with the therapy canine started with five to 10 minutes of free play with the canine, followed by sensory integration therapy based on the child's identified sensory profile. Participants then entered the clinic room for 20 to 30 minutes of a seated activity in which the therapist who taught coping and socialization strategies to participants and caregivers. Sessions concluded with five minutes of play with the canine. Play activities include fetch, soccer, hide and seek, and puzzles. The canine was trained to lay under the table in the clinic room while the therapist was working with the participants. He would provide grounding, light pressure, and deep pressure therapy if the participant became anxious during the sessions. The seated work was recorded using two cameras to ensure visibility of the interactions between the participant and therapist, canine, and caregiver; participant vocalizations and verbalizations; and participant facial expressions. We used two human-animal ethograms to code behavior during sessions and two behavioral assessments to note behavior occurring after sessions. All sessions occurred in the clinic located on the university's campus. Demographic data including participant age, gender, race, ethnicity, referral source, prior medical diagnoses, age of ASD diagnosis, medications, and prior allied health, school, or psychological evaluations. The canine was certified as a therapy dog and service dog certified in 10 ASD service dog tasks at the time of the study. The canine was present during sessions to interact with children and assist them to practice and develop skills to address identified deficits in social-emotional and adaptive functioning, prosocial behavior, and emotional regulation. AAT sessions were recorded to code interactions at a later time.

Objectives

This study will address the following research questions:

1. How do children with autism ages 2 to 18 years interact with a live canine during AAT sessions?
2. How do children with autism ages 2 to 18 years interact with a toy plush dog during AAT sessions?
3. Is there a difference in HAI in the live canine group and the toy plush dog group?
4. Is there a difference in prosocial behavior observed during AAT sessions between the live canine group and the toy plush dog group?
5. Is there a difference in behavior after AAT sessions between the live canine group and the toy plush dog group?

Design and Statistical Analysis Plan

We used two human-animal ethograms to investigate human-animal interaction and bonding occurring during AAT sessions. Prosocial behavior and emotional regulation demonstrated by participants outside of AAT sessions were assessed by two self-report questionnaires completed by caregivers. SPSS and Microsoft Excel were used to calculate the analysis. Descriptive statistics were utilized to compare prosocial behavior and emotional regulation occurring apart from AAT sessions between the two groups. Poisson analysis was conducted to examine human-animal bonding and human behavior occurring during AAT sessions. Independent *t*-tests were used to analyze the differences in human-animal interaction between the two groups. The homogeneity of the variance (HOV) assumption between two groups was checked using Levene's test for equality of variances in SPSS program before conducting the *t*-tests analysis. Results of *t*-tests with adjusted degrees of freedom value were reported if the HOV was violated. The null hypothesis was set to reflect no significant difference in HAI between groups for the independent *t*-tests; therefore, a significant difference in the human-animal interaction and human behaviors regarding the inclusion or exclusion of the canine could be confirmed if the *t*-test results reject the null hypothesis. Cohen's *d* was used to report the effect sizes of the independent *t*-tests; values up to 0.20 were interpreted as small, 0.50 as medium, and 0.80 as large effect sizes. Analysis of variance was used to assess differences between the two groups in prosocial behavior and emotional regulation occurring apart from AAT sessions.

Methods

Demographic data; past, family, and social histories; and prior therapy evaluations were collected during the initial consultation for enrollment into the ASD program. Additionally, pet ownership in the family home was included in the analysis.

The Observation for Human Canine Interaction for Research (OHAIRE) Coding System from University of Arizona was used to note human bonding and prosocial behavior occurring during AAT sessions. The OHAIRE Coding System was specifically created for use in research with participants aged 4 to 16 years but may also be suitable for individuals of other ages, provided appropriate validity and reliability analyses are conducted. Participants must be with at least one

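### 3-AAT frequency is a raw tally with no time base although observed minutes vary between children, so any analysis of tallies should be per coded minute

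*Combined protocol and SAP*

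**What the plan says.** The Methods section records 3-AAT frequency by counting occurrences, in six domains that include affection and play. It gives no divisor and names no part of the session. The duration it records is that of each interaction, not the time under observation. OHAIRE, by contrast, is scored per 10-second interval and summed per 1-minute segment (0 to 36).

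Observed time is not constant. The Clinical Study Description says "Therapy sessions lasted 30 to 45 minutes, depending on the age and ability of the participant" and "Participants then entered the clinic room for 20 to 30 minutes of a seated activity". It times play only for the live arm: "Sessions with the therapy canine started with five to 10 minutes of free play with the canine" and "Sessions concluded with five minutes of play with the canine". For both arms it says "All participants, no matter their group, received the same therapeutic strategies". The plush timetable is not given.

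The Design and Statistical Analysis Plan says "Poisson analysis was conducted to examine human-animal bonding and human behavior occurring during AAT sessions" and adds independent t-tests for human-animal interaction. It mentions no offset, rate or session component for either. It then says that, if the null is rejected, "a significant difference in the human-animal interaction and human behaviors regarding the inclusion or exclusion of the canine could be confirmed".

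**The concern.** A tally grows with the time over which it is taken. If 3-AAT tallies are compared without a time base, children seen for longer score higher at the same behaviour. Within groups this is noise. Between groups it is bias whenever mean coded minutes differ, and the plan would attribute the result to the dog. Session length follows age and ability, and the documents say only that participants were divided into two groups, without a method. Balance in minutes therefore cannot be taken for granted.

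The timed play raises a second, more conditional issue. If play was coded and the plush group had less of it, a difference for research question 3 could partly reflect the mix of activities rather than the response to dog or plush.

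**Working it through.** The plan has no figure of its own to reproduce here. The inputs are the minutes in the Clinical Study Description and the session length in the IRB questionnaire (about 30 to 60 minutes).

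**1. Do the canine-session parts add up?** Opening play + seated work + closing play: 5 + 20 + 5 = 30 and 10 + 30 + 5 = 45 minutes. This matches the stated 30 to 45 only if sensory integration takes no time. Described play is 10 to 15 minutes. A share of one third (10/30, 15/45) leaves nothing for sensory integration; 10/45 = 22% leaves some; 10/60 = 17% applies at the questionnaire's upper limit.

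**2. Exposure.** Expected tally = rate × coded minutes, so at equal rates the ratio of tallies is the ratio of minutes. Whole sessions: 45/30 = 1.5. Seated work only: 30/20 = 1.5. This is a range between children, not a group difference.

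**3. Noise.** Assume minutes spread evenly over 30 to 45, 0.5 events per minute, a between-child coefficient of variation (CV) of 0.5, and minutes unrelated to rate.
- Squared CV of minutes: (15/√12 ÷ 37.5)² = 0.0133.
- Mean tally: 0.5 × 37.5 = 18.75.
- Squared CV of the tally with constant minutes: 0.25 + 1/18.75 = 0.303.
- With varying minutes: (1.25 × 1.0133 − 1) + 1/18.75 = 0.320.

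Variance rises by about 5.5%, so noise alone is modest.

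**4. Bias if mean minutes differ.** This is an illustrative simulation with the same rate and CV, identical rates in both groups, a Welch t-test at two-sided 0.05, and 4,000 runs per setting. The largest group size, 75, is half of the 150 children listed in the IRB record. Rejection rates on raw tallies:

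| Ratio of mean minutes | 15 per group | 30 per group | 75 per group |
|---|---|---|---|
| 1.00 | 5% | 5% | 6% |
| 1.11 | 8% | 11% | 21% |
| 1.25 | 18% | 32% | 67% |
| 1.50 | 47% | 79% | over 99% |

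On tallies per minute, rejection is 4.6% to 5.5% throughout. With equal minutes, raw tallies do no harm.

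**5. Play mix.** Assume no true difference, equal 30-minute sessions, 10 minutes of canine play, p minutes of plush play, and a tally rate in play r times that elsewhere. Live/plush ratio = (10r + 20)/(pr + 30 − p).
- p = 0: r = 0.5 gives 25/30 = 0.83; r = 1 gives 1.00; r = 2 gives 40/30 = 1.33.
- p = 5: r = 2 gives 40/35 = 1.14.
- p = 10: 1.00 for any r.

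In a 45-minute session that leaves time for sensory integration, p = 0 and r = 2 give (20 + 35)/45 = 1.22. Both p and r are assumed, so these ratios show direction and mechanism only. Because session length is equal here, an offset for total minutes would leave them unchanged.

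**The case against.** **Tallies may never be compared.** The plan attaches the Poisson analysis to bonding and human behaviour, and the Methods assign bonding to OHAIRE, which has a fixed time base. The t-tests concern human-animal interaction, and the only 3-AAT input that the Methods name for analysis is the mode, in the sentence on intensity. This reading is possible. It is not settled, because the Methods also describe the 3-AAT as measuring subdomains of human behaviour by frequency. The point therefore applies only where tallies are analysed.

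**Nothing shows that minutes differ by group.** This is correct. Session length is tied to age and ability and is stated before the groups are separated, so a group bias is a possibility and not a finding.

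**A short plan may simply omit the offset.** This also stands. In that case the remedy is a sentence.

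**A reader might infer that the plush group had no play, or less.** The documents do not support that. They are silent on the plush timetable, say that therapeutic strategies were the same, and in the IRB questionnaire offer both groups intermittent interaction in the same words.

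**A reader might also infer that play was coded.** "The seated work was recorded using two cameras" points the other way. The data-collection answer in the questionnaire says all sessions would be recorded, and the OHAIRE text refers to unstructured interaction. If only seated work was coded, the play argument drops out and the varying seated minutes remain.

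**Conclusion.** The point holds for 3-AAT frequency wherever tallies are analysed. The stated method has no time base for a count taken over minutes that can differ 1.5-fold between children. The certain consequence is some avoidable noise, modest under the assumptions above. Bias arises only if mean coded minutes differ by group. A part due to play needs coded play footage, shorter plush play and a tally rate that differs in play. None of these conditions is established, so size and direction are unknown.

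Modal intensity does not grow with minutes. OHAIRE is exposed only through which part of the session its segments come from. It would go too far to conclude that the live-versus-plush comparison is biased, or that questions 3 and 4 should rest on seated work alone. During seated work the dog was trained to lie under the table, and play is arguably part of the live-dog intervention.

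**What to change.** - Take coded minutes for each child from the existing video, over the same footage as the tallies.
- Fit the Poisson analysis of 3-AAT counts with a log link and a log(coded minutes) offset. Use tallies per coded minute in any t-test on frequency.
- State the plush timetable, which footage was coded, and which 3-AAT variable each test uses.
- If play was coded, also report the comparison separately for play and for seated work, as a supporting analysis. A total-minutes offset does not correct for a different mix of components.
- If play time differs by group, describe a whole-session difference as one between session packages, not as the effect of the dog alone.

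The offset handles observed time only; extra variation between children is a separate matter. The cost is a short text edit and some time-marking, for which the ELAN software already in the plan may serve. The documents do not say that 3-AAT tallies were time-stamped. If they were not, a split by component would need some re-coding from video. No new participants are required.

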Lastly, the Positive and Negative Affect Schedule (PANAS) was administered weekly to measure therapeutic effects occurring in everyday life outside of the AAT session. The PANAS is a 20-item questionnaire utilizing a 5-point Likert scale to assess positive and negative affect occurring the week prior to administration. Each domain has 10 items with scores ranging from 10 to 50, with lower scores reflecting lower levels of positive or negative affect and higher scores signifying higher positive or negative affect. Total scores on each scale are obtained by adding the scores for each item. Analysis of the PANAS demonstrates very good internal consistency reliability, with alphas ranging from 0.86 to 0.90 for Positive affect and from 0.84 to 0.87 for Negative affect.

Protocol Number: 2307483365
Investigator: [name]

Expiration Date: 10/10/2025
Last Approval Date: 10/11/2024

University of Arkansas System

Document Overview

Description: Human animal interaction between children and a live canine or toy plush dog
Explanation:
Organization Doc Num:

Protocol Summary

Protocol Number: 2307483365
Sequence Number: 3
Status: Active - Open to Enrollment
Expiration Date: 10/10/2025
Last Approval Date: 10/11/2024
Investigator: [name]

Protocol Details

Type: Expedited
Summary/Keywords:
Application Date: 09/21/2024
Reference ID1:
Reference ID2:
FDA Application No:
Title: Human animal interaction between children with ASD and a live canine or plush toy dog

Areas of Research

Code	Description
000001	All Research Areas

Organizations

Type	Organization	Address
Performing Organization	University of Arkansas	University of Arkansas [name] USA

Funding Source

Type	Number/Code	Source	Title
Internally Funded/ Unfunded Research	unfunded	N/A	

Protocol Number: 2307483365
Investigator: [name]

Expiration Date: 10/10/2025
Last Approval Date: 10/11/2024

Subjects

Subject	Count
Children	150

Investigators

Person Name: [name] **Role:** Principal Investigator
Units: CC012723 UAF | NURS | Department of Nursing **Affiliation:** Supervisor
Office [contact] **Mobile:**
Email: [contact]

Study Personnel

Person Name	Role	Affiliation	Email
[name]	Study Personnel	Non-Faculty	[contact]
[name]	Study Personnel	Student Investigator	[contact]
[name]	Study Personnel	Student Investigator	[contact]

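### The only analysis plan is dated more than six months after the stated end of the study and reports the tests as already run, so the documents do not show pre-specification and do not support confirmatory wording

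*Combined protocol and SAP*

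**What the plan says.** The cover page carries "Date: March 13, 2025". The Clinical Study Description says "The study was conducted between June 2022 through August 2024" and describes the aim as exploring gaps in knowledge.

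The Design and Statistical Analysis Plan section gives its analysis steps in the past tense: "SPSS and Microsoft Excel were used to calculate the analysis"; "Independent *t*-tests were used to analyze the differences in human-animal interaction between the two groups"; "Results of *t*-tests with adjusted degrees of freedom value were reported if the HOV was violated". Poisson analysis, descriptive statistics and analysis of variance are described the same way. The section then says that a significant difference "could be confirmed if the *t*-test results reject the null hypothesis". It names no primary outcome, time point, alpha or multiplicity rule.

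The IRB application is written prospectively. Its Questionnaire lists the same five research questions, three of them live canine against plush toy. It names OHAIRE, the 3-AAT ethogram, the SDQ and the PANAS, and says that an OHAIRE bond score will be calculated. It contains no statistical methods. Its Protocol Summary reads "Status: Active - Open to Enrollment".

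**The concern.** A plan supports a confirmatory claim only if it can be shown to precede sight of the data. Here the section headed as a plan reads as a methods report and post-dates the stated study period, and nothing earlier in the documents specifies an analysis.

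There was real room for choice. Under Methods, the 3-AAT ethogram yields frequency, duration and intensity across six domains and 24 subdomains, and the analysis section does not say which of these answers the question on human-animal interaction. Poisson analysis and t-tests are both assigned to overlapping in-session constructs. Descriptive statistics and analysis of variance are both assigned to behavior outside sessions. If such choices are made after the results are visible, the p-values lose their nominal error rate and a reader cannot tell a planned comparison from a selected one. Adding an alpha, a multiplicity rule or random allocation would not repair this, because the problem is timing.

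**Working it through.** The plan gives no alpha, power or sample-size calculation, so there is no figure of its own to reproduce. The check is of dates, then of content, then of possible size.

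**1. Gap between the stated end and the document date.** Inputs: August 2024 (Clinical Study Description) and 13 March 2025 (cover page).
- From 31 August 2024: 30 + 31 + 30 + 31 + 31 + 28 + 13 = 194 days, and 194 / 30.4375 = 6.4 months.
- From 1 August 2024: 194 + 30 = 224 days, or 7.4 months.

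The gap exceeds six months on either reading of August.

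**2. Whether the IRB record shows anything earlier.** Inputs: the Actions table and the Protocol Summary.
- Record created 29 July 2023: 394 to 423 days after the June 2022 start (counted from 30 June and 1 June).
- First approval 19 September 2023: 446 to 475 days after the start.
- The printed application is sequence 3, with application date 21 September 2024: 21 to 51 days after the stated end.

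The record was opened during the stated study period, but the printed text cannot be dated earlier than its own application date. It therefore does not show when the research questions were first written.

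**3. What each part fixes.**

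| Item | IRB application | Analysis plan section |
|---|---|---|
| Group comparison of interest | Yes, as open questions | Yes |
| Instruments | Yes | Ethograms and questionnaires mentioned generally (named under Methods) |
| OHAIRE bond score | Yes | Defined under Methods |
| Which 3-AAT summary answers the question | No | No (Methods says that a mode was entered) |
| Test | No | Yes, in the past tense |
| Time point, alpha | No | No |
| Decision rule | No | Rejection by t-test, no level given |

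**4. Possible size, for illustration only.** Assume a two-sided 5% level, one 3-AAT domain, three candidate summaries (count, duration, intensity), no true difference, and free choice of the summary to feature.
- Uncorrelated summaries: 1 − 0.95³ = 0.143.
- Equal correlation r: 1 − ∫ φ(t) [Φ((1.96 − √r·t)/√(1−r)) − Φ((−1.96 − √r·t)/√(1−r))]³ dt. Numerical integration gives 0.125 at r = 0.5 and 0.098 at r = 0.8.

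The range is therefore 9.8% to 14.3% against a nominal 5%. The level, the correlations and the free choice are all assumptions; none is stated in the documents.

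**The case against.** The strongest reply is that late documentation is not late choice. The cover date is the date of the document, not a recorded date on which tests were selected. Sessions were recorded for coding at a later time and no coding or analysis date is given, so when anyone saw the ethogram data is unknown. This stands. A reader might infer that no comparison was fixed before the data were seen. The documents show only that there is no evidence of it.

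A second reply is that the IRB application does specify something. It poses the group comparisons and names the bond score. A protocol note of 30 July 2023 says that OHAIRE will be used for human-animal interaction, and the PANAS and 3-AAT attachments bear the same date, about 13 months before the stated end. This also stands: it would be wrong to say that the application contains no comparison or outcome score. But it gives no test, time point or decision rule, and even July 2023 falls after the stated start.

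Third, Methods says that the mode was entered for analysis, which might settle the 3-AAT summary. That sentence may refer to intensity alone, and it is in the past tense too. No document shows that summaries were selected by result, so the error rates above are not an estimate of what happened.

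Fourth, the sentence on confirming a difference may be no more than loose language for rejecting a null hypothesis, given the exploratory aim. If so, rewording it costs nothing.

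**Conclusion.** The concern holds in a limited form. The only analysis plan is dated 194 to 224 days after the stated end of the study and reports its tests as done. It therefore cannot serve as evidence that any test, or any choice among the 3-AAT summaries, was fixed before the data were seen. The statement that a difference "regarding the inclusion or exclusion of the canine could be confirmed" is unsupported and conflicts with the stated exploratory purpose.

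This rests on taking August 2024 as the end of the study. The Protocol Summary's open-to-enrollment status, under an approval of 11 October 2024, does not sit easily with that date, and the two must be reconciled. It also rests on there being no earlier dated plan outside these documents; producing one could settle the matter.

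The documents do not support the stronger inference that analyses were chosen to suit the results. Nor do they support reading 9.8% to 14.3% as the study's actual error rate.

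**What to change.** 1. In the Design and Statistical Analysis Plan section, state when the outcomes, summaries and tests were chosen relative to data collection and to the coding of the recordings. If an earlier dated plan exists, cite and append it.
2. Unless one is produced, label the June 2022 to August 2024 comparisons exploratory, report estimates with 95% intervals, and replace the phrase *could be confirmed* by *would suggest, for later confirmation*.
3. Reconcile the August 2024 end in the Clinical Study Description with the enrollment status in the Protocol Summary.
4. If more children are enrolled, write down one outcome, one summary and one test per question, and date that text on the day it is written. Confirmatory wording may then apply only to children enrolled after that date, analyzed separately from the earlier data. It must not be backdated to 13 March 2025, because the present section does not make those choices. If no more children are enrolled, the study stays exploratory.

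Items 1 to 3 need only wording and a check of the records; the price is a weaker claim for the existing data. Item 4 creates a new analysis set of unknown size, because the documents do not say how many of the 150 approved children are already enrolled.
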